
45 to 64. Over the past decade, the smartphone has become an integral part of most people's lives. The latest Pew Research Data from February 2018 shows that 73% of individuals aged 50 to 64 own a smartphone (8). Smartphones would allow the patient to have direct multimedia access to a prescriptive exercise program designed by a licensed Physical Therapist without an in-person home visit, as well as to have communication directly with their Physical Therapist through secure in-app messaging or e-mail. The patient would benefit by having reduced intrusion in their home environment, convenient access to their Physical Therapist and their Physical Therapist's plan of care, and financial savings due to the elimination of home health care services following TKA. The Physical Therapist would benefit from the ability to quickly interact with the patient to mitigate any adverse events and to efficiently assist a greater number of patients compared to traditional home-based physical therapy. Third-party payors would benefit from drastically reduced home care costs for those recovering from TKA.

Objectives

The primary objective will be to determine the efficacy of the app for those recovering from TKA compared to traditional home care during the home bound portion of the patient's recovery from TKA by comparing ROM improvement outcomes between the intervention group and the control, as well as measuring the subjective improvement in functional outcomes for the intervention group by using the Short MAC. A secondary objective of the study is to determine the relationship between the intervention participants' self-reported frequency of engagement with the app and their qualitative and quantitative outcomes, otherwise known as the dose-response.

Methods

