The intervention group for this study are those who will utilize the smartphone app to complete the home-based portion of physical therapy following TKA. The control group are those who have completed traditional home health physical therapy following TKA. Inclusion criteria for the study consists of participants aged 45 to 64, the participant will have undergone unilateral TKA, and the participant should be discharged directly to home from the hospital. Participant's data from the intervention group will be excluded from the study if they do not engage with the app within 24 hours of discharge from the hospital, if the participant neglects to engage with the app over any 24-hour period during the study, or if the participant is readmitted to the hospital at any point during the home bound portion of their recovery.

Subjective outcomes for the participants in the intervention group will be assessed by the Short MAC and objective outcomes will be assessed by measuring total knee ROM improvement. The intervention participants' self-reported frequency of app usage will be compared to the participants' outcomes to determine the dose-response of the app. The Short MAC has been previously shown to be a reliable, valid, and responsive indicator of qualitative improvement in a patient's functional status post-TKA and total hip arthroplasty (THA) by Whitehouse et al (1). Minimum important change for Short MAC has been found to be 7.9 points for small change, 8.4 points for medium change, and 12.1 points for large change (2). The total knee ROM

improvement in the treatment group will be compared against a control group of patients who have completed traditional home care from a variety of physical therapists following TKA.

The primary hypothesis is that the intervention group will show a statistically equal outcome to the control group, demonstrating the efficacy of a low-cost alternative to traditional home care. The null hypothesis is that the research group will not show a statistically equal outcome to the control group. The first alternative hypothesis is that the intervention group will show a statistically significant improvement over the control group. The second alternative hypothesis is that the control group will show a statistically significant improvement over the intervention group.

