Data for the control group will be taken from approximately 30 individuals aged 45 to 64 that have previously completed traditional home health physical therapy care from a variety of physical therapists following TKA. Data for the intervention group will be taken within 48 hours of being discharged from the hospital from approximately 30 participants who agree to use the smartphone app to complete the home-based physical therapy portion of their recovery from TKA. Intervention group participants will complete an introductory meeting with the physical therapist in-person to onboard the patient to the app and perform the initial data collection. Participants in the intervention group will be encouraged to engage with the app 3 to 5 times per day as able. The intervention participant will have the ability to communicate any questions or concerns to the Physical Therapist via e-mail or phone call throughout the homebound portion of their recovery. For safety monitoring, a physical therapist will contact the intervention group participant via phone or e-mail every 24 to 48 hours to ensure no adverse events have occurred. A final in-person meeting will occur between the Physical Therapist and the participant at the conclusion of the homebound portion of the participants' recovery for the purpose of final data collection. A two-tailed t-test for two independent groups will be used to compare the means for total ROM improvement between the intervention group and the control group. Data from the Short MAC will be used to describe the overall subjective effect of the intervention on the patient's functional abilities. The relationship between the Participants self-reported frequency of app usage and their combined subjective and objective outcomes will be used to understand the dose-response of the app. Information about dose-response will be integral in establishing guidelines regarding frequency of app usage for optimal results.

Conclusion

Traditional home health care for individuals recovering from unilateral TKA is expensive and provides a higher level of service than most individuals, aged 45 to 64, require. Use of smartphone technology has the potential to drive down costs while maintaining outcomes for this patient population. The proposed randomized controlled trial would determine the efficacy and proper dose-response of a smartphone app to reduce costs and maintain outcomes for the desired patient population compared to traditional home care.

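### Short MAC measured only in app users cannot serve an efficacy objective set against home care, and unassigned, self-reported app use yields an association rather than a dose-response

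*Protocol*

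**What the plan says.** **Short MAC.** The Protocol's Objectives section sets one primary objective: efficacy of the app relative to traditional home care. It is to be met by comparing ROM improvement between groups and also by "measuring the subjective improvement in functional outcomes for the intervention group by using the Short MAC". The Methods repeat the restriction to one group: "Subjective outcomes for the participants in the intervention group will be assessed by the Short MAC". Later in the Methods: "Data from the Short MAC will be used to describe the overall subjective effect of the intervention on the patient's functional abilities". The one between-group analysis is a two-tailed t-test that "will be used to compare the means for total ROM improvement between the intervention group and the control group". No Short MAC data are planned for the controls, who are described as having already finished home care.

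**Dose-response.** The secondary objective concerns the relationship between frequency of engagement and outcomes. The Methods go further: "self-reported frequency of app usage will be compared to the participants' outcomes to determine the dose-response of the app". They add that this information will be integral to guidance on how often to use the app for the best results. The Conclusion says the trial would establish the proper dose-response. Frequency is not assigned: "Participants in the intervention group will be encouraged to engage with the app 3 to 5 times per day as able". Two exclusion rules in the Methods remove app users for non-engagement: one for no engagement within 24 hours of discharge, the other for a gap over any 24-hour period. A third, for hospital readmission, is not at issue here.

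**The concern.** Two claims go beyond what the design can deliver.

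First, a change from before to after in a single group counts towards an objective that is comparative by its own wording, and is described as an effect of the intervention. After knee arthroplasty, function can be expected to improve over the homebound weeks whatever the mode of therapy. A reader could take a good Short MAC change as support for the app against home care when nothing collected bears on that.

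Second, guidance on frequency of use would draw on participants' own choices. A person recovering well may use the app more because exercise is easier. A person struggling may use it more because they are worried. Either way the outcome helps to determine the supposed dose, and the analysis cannot tell which pattern is present.

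**Working it through.** The Protocol gives no figure to reproduce on this point: no standard deviation, effect size, power or margin. The check is what each planned measurement can identify.

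**1. Short MAC**

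| Outcome | App users | Controls | Between-group test |
|---|---|---|---|
| ROM improvement | about 30 | about 30 | two-tailed t-test |
| Short MAC | about 30 | 0 | none |

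Write the mean change in app users as N + A, where N is ordinary recovery and A is what the app adds. The change under home care is N + H. The comparative objective needs (N + A) - (N + H) = A - H. Only N + A is observed. More app users would estimate N + A more precisely but would say nothing about A - H, nor about A alone.

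**2. Dose-response: direction of bias**

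Take a standardised model: outcome = β × use + g × pace of recovery + error, with corr(use, pace) = a. The expected correlation of use with outcome is then r = β + g × a. All inputs below are assumed, because the Protocol gives none of them. Set g = 0.5.

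| β (true effect of use) | a | r = β + 0.5 × a |
|---|---|---|
| 0 | +0.5 | +0.25 |
| 0 | -0.5 | -0.25 |
| 0.25 | +0.5 | 0.50 |
| 0.25 | -0.5 | 0.00 |

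The same design can show an effect where none exists, or hide one that does. The table shows that the sign of the bias is unknown. It does not estimate its size.

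**3. Dose-response: truncation, self-report and precision**

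The two non-engagement rules remove participants with days of no use. Regular users at a low daily frequency stay in, so the low end is cut but not emptied. In a simulation with a true correlation of 0.50 (assumed):

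- self-report reliability of 0.7 (assumed) reduces it to about 0.42;
- removing the lowest 25% of users (assumed) reduces it to about 0.39;
- both together reduce it to about 0.29.

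For precision, with n = 30 and an observed r of 0.3, the Fisher interval is tanh(atanh(0.3) ± 1.96/√27) = tanh(0.310 ± 0.377), or about -0.07 to 0.60. Even without bias, at most about 30 people would not fix a frequency.

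**4. Can an analysis plan supply what is missing?**

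No. The one-group measurement and the unassigned, self-reported use are fixed in the Protocol. Baseline adjustment can reduce confounding by starting condition. It does not remove reverse causation during recovery.

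**The case against.** The Protocol is open about much of this. It says twice that the Short MAC is for the intervention group, it uses the verb *describe*, and no test or decision rule depends on it. The secondary objective speaks of a relationship, which is a fair term. Calling the information integral to guidelines does not say that this trial alone would set them. Dose-response is secondary, and interval estimates and covariates are normally left to an analysis plan, which is not at hand.

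Most of this stands, and it limits the point to the claims themselves: the place of Short MAC in a comparative primary objective, the word *effect*, and the stated intention to determine a proper dose-response.

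Three stronger readings are tempting, and the document does not support them:

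- *The minimum important changes will be used to judge the app against home care.* The Methods list "7.9 points for small change, 8.4 points for medium change, and 12.1 points for large change" but never say that passing one of these shows anything relative to home care.
- *A between-group Short MAC claim is concealed.* None is planned, and the restriction to app users is stated plainly.
- *The dose-response will be inflated.* The direction is not known. The phrase *as able* ties use to the participant's condition without saying which way.

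**Conclusion.** The point holds in this limited form. Short MAC, with 0 of about 30 controls measured, cannot contribute to an objective defined against home care and cannot be called an effect of the intervention. App use that is self-chosen, self-reported and truncated supports an exploratory association only. It does not support a determined or proper dose-response, nor guidance on the best frequency.

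The Short MAC conclusion follows from the Protocol's text and needs no numerical assumption. The dose-response conclusion rests on use being unassigned, which the Protocol states. The correlations shown are illustrations under assumed inputs.

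The planned ROM comparison is not affected by this point. The wording should be corrected before results are reported, because as it stands an uncontrolled change could be read as comparative efficacy.

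**What to change.** 1. Move Short MAC out of the comparative primary objective and make it a descriptive secondary outcome in app users. In the Methods, replace the reference to an effect of the intervention with change during the homebound period. Adding control Short MAC is not a practical alternative: the controls, as described, have already completed care, so their early scores could not be collected prospectively.
2. Restate dose-response as an exploratory association, adjusted for the baseline value of the outcome analysed: ROM, and Short MAC where the initial data collection includes it. The Protocol says app users "complete an introductory meeting with the physical therapist in-person to onboard the patient to the app and perform the initial data collection" but does not list Short MAC there. A baseline is implied by the term improvement, so this should be confirmed. State that adjustment does not remove reverse causation.
3. For this analysis only, keep app users who would be excluded solely for non-engagement, under either 24-hour rule, where a final measurement exists. Report how many are recovered. The number may be small, because the Protocol does not say that excluded participants are still measured. Lifting only one of the two rules would be inconsistent, since both remove low users.
4. In the Methods and Conclusion, replace *determine* and *proper dose-response* with *explore the association*. Soften the guideline sentence to say that the result can inform a later randomised comparison of frequencies.

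**Cost.** Items 1 and 4 are wording. Items 2 and 3 use data from the planned initial and final meetings and add no visit, provided the Short MAC baseline is in fact taken. The price is a more modest claim.

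### The dose-response pairs self-reported app use with an outcome that includes the Short MAC, so error shared by the two reports can create a positive relationship; ROM dilutes this if merged but does not remove it

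*Protocol*

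**What the plan says.** The Objectives section names the dose-response as a secondary objective, confined to the intervention group. Methods fixes the source of the dose: "The intervention participants' self-reported frequency of app usage will be compared to the participants' outcomes to determine the dose-response of the app". No app log or other record of use is named.

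The outcomes come in two kinds. Of the first, Methods says: "Subjective outcomes for the participants in the intervention group will be assessed by the Short MAC". The second, which Methods calls objective, is the measured gain in knee ROM. For the dose-response the two are brought together: "The relationship between the Participants self-reported frequency of app usage and their combined subjective and objective outcomes will be used to understand the dose-response".

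The two occasions described for collecting data are both with a physical therapist. The first is an "introductory meeting with the physical therapist in-person to onboard the patient to the app and perform the initial data collection". The second is described thus: "A final in-person meeting will occur between the Physical Therapist and the participant at the conclusion of the homebound portion", for the final data collection. In between, a physical therapist phones or e-mails every 24 to 48 hours to check for adverse events.

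Participants "will be encouraged to engage with the app 3 to 5 times per day as able", and Methods excludes the data of anyone who goes 24 hours without engaging. Methods also says the dose-response result is to be integral to guidelines on how often to use the app.

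**The concern.** Purely random error in reported use would normally weaken a dose-response. Error shared by reported use and reported improvement behaves differently: it pushes the correlation upward and can produce one where use has no effect. A larger sample does not cure this; it only makes the artefact easier to declare significant.

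The design gives some reason to overstate use: there is a stated daily target, and a 24-hour gap leads to exclusion. A participant who wishes to appear diligent and improved, in front of a clinician, can shade both answers the same way. If the Short MAC is merged with ROM, that error enters the merged outcome. At stake is the use made of the result: an artefact of reporting could be turned into advice on frequency of use.

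**Working it through.** The protocol gives no figure for the dose-response (no test, alpha, effect size or SD), so there is nothing to reproduce. The calculation below is an illustration.

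**From the protocol (Methods)**
- About 30 intervention participants, before exclusions.
- Dose: self-reported frequency of use.
- Outcomes: Short MAC (subjective) and ROM improvement (measured), taken in combination.

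**Assumed**
- Pearson correlation tested at two-sided 0.05, counting only significant positive results (2.5% nominal).
- No true effect of use.
- One reporting tendency explains a share s of the variance of reported use and the same share of the variance of Short MAC improvement; s = 0.1, 0.2, 0.3.
- ROM is independent of that tendency and uncorrelated with the Short MAC.
- If merged, the two standardised outcomes have equal weight.

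**Expected correlation with reported use**
- Short MAC alone: each report carries the tendency with loading √s, so r = √s × √s = s.
- Equal-weight combination: the covariance is still s, but the sum of two independent unit-variance outcomes has SD √2, so r = s/√2.
- ROM alone: r = 0.

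**Chance of a significant positive result** (Fisher z): P(Z > 1.96 − atanh(r) × √(n − 3)), with √27 = 5.196 for n = 30.

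| s | Outcome | r | atanh(r) × 5.196 | Chance |
|---|---|---|---|---|
| 0.1 | Short MAC | 0.100 | 0.521 | 0.075 |
| 0.2 | Short MAC | 0.200 | 1.053 | 0.18 |
| 0.3 | Short MAC | 0.300 | 1.608 | 0.36 |
| 0.1 | Combined | 0.071 | 0.368 | 0.056 |
| 0.2 | Combined | 0.141 | 0.740 | 0.11 |
| 0.3 | Combined | 0.212 | 1.119 | 0.20 |

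If exclusions left 20 participants (√17 = 4.123), s = 0.2 and 0.3 give 0.13 and 0.25 for the Short MAC alone, and 0.085 and 0.14 for the combination.

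**Check by simulation** (20,000 runs, n = 30, rejections in either direction, 5% nominal): 8%, 19% and 37% for the Short MAC alone; 7%, 11% and 20% for the combination; about 5% throughout for ROM alone. These agree with the formula.

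**Which way the assumptions lean.** Improvement is a difference between the initial and final scores. A tendency that is the same at both visits shifts both scores and partly cancels, so the share s left in the improvement is likely to be smaller than the share in either score. A positive correlation ρ between Short MAC and ROM improvement lowers the combined figure further, to r = s/√(2(1 + ρ)). The figures are therefore at the upper end for a given strength of tendency.

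**The case against.** **The combined outcome may not be a composite.** The protocol never defines a merged score. The Objectives section speaks of qualitative and quantitative outcomes, and the wording in Methods could mean that both are looked at side by side. An SAP not shown may settle this. That stands. If the outcomes are analysed separately, ROM is not contaminated through merging, and the concern narrows to the Short MAC relationship.

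**No test is stated and s is unknown.** Also correct. The percentages show how the mechanism scales; they do not predict this trial.

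**Points a reader might infer that the text does not support.**
- That one therapist runs the app, makes the contacts and collects all the data. The protocol does not say so.
- That the phone and e-mail contacts collect use or outcome data. Their stated purpose is safety.
- That the Short MAC is completed in front of the therapist. The protocol does not say how it is completed, nor to whom or when use is reported.
- That the Short MAC rates (8%, 18%, 36%) apply to the planned combined outcome. On an equal-weight reading they fall to about 6%, 11% and 20%.

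**ROM is not a full remedy.** It avoids the shared-report channel only. No blinding of the person measuring ROM is described, and use is not randomised: participants use the app as able, so those recovering well may simply use it more. This stands, and it limits what any dose-response from this design can support.

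**It is a secondary, single-arm analysis.** True; the primary ROM comparison between groups is unaffected. The stated plan to base usage guidelines on it is what makes the point worth acting on.

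**Conclusion.** The concern holds in a limited form. The protocol itself fixes a self-reported dose and relates it to outcomes that include the Short MAC, so a reporting tendency shared by the two can create a positive relationship where none exists. If the outcomes are merged with equal weight, ROM cuts the expected spurious correlation by a factor of √2 but leaves the chance of a false positive finding at about 6% to 20% for s between 0.1 and 0.3, against 2.5%.

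This rests on reading the Short MAC as self-report, on an assumed Pearson test and on an assumed s. The documents do not show that such a tendency is present, only that the plan has no protection against it. A later choice of model could separate the outcomes, but could not remove the tendency from a dose known only by self-report. The point is worth correcting because of the intended guideline and because the change is cheap.

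**What to change.** In Methods, where the dose-response analysis is described:

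1. Replace the combined outcome with two separate analyses: reported use against ROM improvement as the lead analysis, and reported use against Short MAC improvement as supportive only.
2. State that, because use is self-reported and not randomised, the dose-response is an association that generates hypotheses and will not by itself set guidelines on frequency of use. Bring the sentence on guidelines in Methods and the dose-response claim in the Conclusion into line with this.
3. Optionally, have participants complete the Short MAC themselves, without the therapist seeing the answers. This reduces the wish to please but does not remove a participant's own reporting tendency.

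The cost is a change of wording and, for the option, a self-completed form. The downsides are a more modest dose-response conclusion and perhaps a few incomplete Short MAC forms.
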